Probe based confocal laser endomicroscopy was first used in gastroenterology (endobrachy oesophagus, bilio-pancreatic lesions, colorectal polyps, inflammatory bowel disease...) (5). In pulmonary medicine pCLE came later to the light and is still an experimental technique but several studies are on going. Domains of interest are numerous:

- Pulmonary nodules evaluation;
- Interstitial lung diseases;
- Lung and bronchus infections;
- Lung rejection after transplantation (6);
- Lung emphysema (7);
- Mediastinal adenopathy (8);
- Pleural malignancies ;

Pleural effusion is a common finding in medical practice and often requires thoracocentesis and pleural biopsies to determine the underlying disease. However, thoracocentesis with pleural fluid cytology has limited sensitivity (up to 60% for repeated thoracocentesis) for a malignant pleural effusion diagnosis, one of the most common cause of pleural effusion (9-11). Therefore, thoracoscopy is often required, allowing direct pleural examination and biopsies with a sensitivity and a specificity of 94% and 100 % for malignant diseases(12,13). Nonetheless, this procedure is more invasive than a simple thoracocentesis. Recently, four studies demonstrated that pleural pCLE could be of value for the diagnosis of malignant pleural effusion. In 2018 Zirlik et al. showed that pCLE with fluoresceine performed in the pleural fluid after thoracocentesis was able to identify a malignant pleural effusion with 87 % sensitivity and 99% specificity compared

pleural fluid cytology (14). In 2019 Wijmans et al. showed that pCLE was able to guide pleural biopsies when the probe was passed through the biopsy needle during a thoracoscopy, an open thoracotomy or an ultra-sound or CT guided pleural biopsy when a malignant pleural mesothelioma was suspected(15). In 2021 our team published a prospective trial showing that pCLE during medial thoracoscopy was able to discriminate malignant from benign pleura(16,17). The same year, Sawada et al. showed that pCLE performed during surgery for lung cancer was able to identify a visceral pleural involvement with 100% sensitivity and 83% specificity(18). Considering these results and the low sensitivity of thoracocentesis for malignant pleural effusion identification, we conducted this proof of concept study to determine if mini-invasive close-blinded pleural pCLE performed through a Boutin's needle was feasible, safe and had a better sensitivity than thoracocentesis.

Study design

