Exploratory study on a diagnostic procedure based on a cross-sectional study. We will prospectively include all patients referred to medical pleuroscopy for pleural effusion treatment or work-up.

The intervention was divided into four parts realized by the two same experienced investigators: First, the thoracocentesis for pleural fluid sampling and pathological examination; Second, the mini-invasive pleural pCLE (Alveoflex ®, lateral resolution 3 μ m, optical area 1.13 mm², depth of focus 0 - 50 μ m) (Cellvizio®, Maunakea technologies®, Paris, France); Third, the invasive pleural pCLE through the thoracoscope; Fourth, the traditional medical thoracoscopy with pleural examinations, biopsies and talc poudrage if required. Two different thoracoscopes were used during this study: A Wolf thoracoscope with an outer diameter of 7 mm (Richard Wolf GmbH, Knittlingen Germany ®) and a Storz single puncture thoracoscope with an outer diameter of 10 mm (Karl Storz GmbH, Tuttlingen, Germany ®). For pleural staining, 5ml of fluorescein 10% were intravenously administrated 5 min before pCLE acquisition. The investigators were aware of the clinical history of the patients during the intervention as it happens in real clinical practice.

For the mini-invasive pleural pCLE, the probe was blindly introduced in the pleural space through the Boutin's needle (traditionally used in medical thoracoscopy to induce a pneumothorax before insertion of the trocar) until satisfying images were recorded. At the same time, the two endoscopists rated 7 criteria (see the table 1 for the criteria and their interpretation). The part three (invasive pleural pCLE) started by the insertion of the trocar allowing to perform the medical thoracoscopy. For this part, the probe was gently applied on the parietal pleura through the working channel of the thoracoscope under vision control. If macroscopic abnormalities were noticed, pCLE was performed on the affected zones. In the absence of macroscopic abnormality, three random sites were selected. The same criteria were rated by the same two investigators. Finally, biopsies were systematically performed on the same sites for pathological diagnosis.

The assessed visual criteria were chosen in accordance with our previous publications and experience(16,17).

Methods

Inclusion/exclusion criteria

Every patient referred to medical thoracoscopy for pleural effusion willing to participate and signing informed consent.

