Exclusion: unwilling to participate or unable to give informed consent; <18 years; pregnant woman; known allergy to fluorescein

Controls:

Pleural fluid cytological analysis

Aims:

To determine the feasibility and safety of mini invasive pleural pCLE assessment

To determine the sensitivity of mini invasive pleural pCLE compared to pleural fluid cytological analysis

Standard demographic, clinical, biological and endoscopic assessment

Gender, age

Medical background

Smoking habit

Current therapy

Blood: CRP, Albumin, total proteins, Hemoglobin, Platelet count, White blood cells, LDH

Pleural fluid: Cytological and bacteriological studies, LDH, Albumin, proteins

Sample size

No formal sample size calculation can be performed for such exploratory study. Every major patient referred for medical pleuroscopy will be proposed the study and screened if they give their informed consent.

Statistical analysis

The Fisher's exact test was used to analyze the link between pCLE qualitative variables and the final histological diagnosis. No adjustments are made for multiple variable testing.

2. Wang TD. Confocal microscopy from the bench to the bedside. *Gastrointestinal endoscopy*. 2005 Nov;62(5):696–7.

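### The only planned test leaves out cytology, so aim 2 (mini-invasive pCLE sensitivity compared with cytology) has no analysis

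*Combined protocol and SAP*

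**What the plan says.** The Aims section has two entries. The first is feasibility and safety. The second reads: "To determine the sensitivity of mini invasive pleural pCLE compared to pleural fluid cytological analysis". The Controls entry is cytology of the pleural fluid and nothing else. The introduction gives the purpose as finding out whether mini-invasive pCLE "was feasible, safe and had a better sensitivity than thoracocentesis".

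The Statistical analysis section has two sentences. One says: "The Fisher's exact test was used to analyze the link between pCLE qualitative variables and the final histological diagnosis". The other says that multiplicity is not adjusted for. Neither mentions sensitivity, a confidence interval, cytology or a comparison of two tests.

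The Study design section sets out a within-patient sequence: "First, the thoracocentesis for pleural fluid sampling and pathological examination; Second, the mini-invasive pleural pCLE", then pCLE through the thoracoscope, then thoracoscopy with systematic biopsies. Two endoscopists rate seven visual criteria, and table 1, which is not shown, is cited for the criteria and how to interpret them.

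**The concern.** Aim 2 is a comparison of two diagnostic tests. The planned analysis relates one of them to histology and never uses the other. A small Fisher p-value would show that a pCLE criterion is associated with malignancy. It would say nothing about cytology, yet it would be the only inferential result beside a stated interest in better sensitivity than thoracocentesis, and could be taken as support for it.

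Followed as written, the plan gives no estimated difference from cytology and no measure of its precision. It also leaves open how non-evaluable or inconclusive results count. Imaging continued "until satisfying images were recorded", and the text does not say what happens when that point is not reached.

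**Working it through.** The plan states no sample size, power or expected sensitivity for this study, so there is no figure to reproduce. The check has four steps.

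**1. Is cytology used in any analysis?** Cytology appears as background, as the first step of the procedure, as the control and as a collected item. It is in no planned analysis. This holds whether cytology is read as the competing test or as the reference for pCLE.

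**2. Does the Fisher result depend on cytology?** Assume 30 malignant and 20 benign patients, with pCLE positive in 26/30 and 2/20. Fisher's exact p is about 6e-8. Let b be the malignant patients positive on pCLE only and c those positive on cytology only. Cytology sensitivity is (26 - b + c)/30.

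| b v c | Cytology sensitivity | pCLE sensitivity | Exact McNemar p |
|---|---|---|---|
| 8 v 0 | 18/30 = 60% | 86.7% | 0.008 |
| 12 v 4 | 18/30 = 60% | 86.7% | 0.077 |
| 4 v 4 | 26/30 = 86.7% | 86.7% | 1.00 |
| 0 v 3 | 29/30 = 96.7% | 86.7% | 0.25 |

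The Fisher p-value is the same in every row. The example uses one overall pCLE call, whereas the plan tests separate pCLE variables. The argument carries over to each variable, because none of those tables contains cytology.

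**3. What do two raw sensitivities leave out?** Assume n = 30 malignant patients, pCLE positive in 24 (80%, assumed) and cytology in 18 (60%). The 60% is the introduction's upper figure, given for repeated thoracocentesis. Exact 95% intervals are 61.4 to 92.3% and 40.6 to 77.3%. The difference is (b - c)/n = 6/30 = +20 points. Only six patients are pCLE-negative, so c can be 0 to 6, which gives seven possible splits.

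The Tango limits are the values of d at which (b - c - nd) / sqrt{n[2q + d(1 - d)]} = ±1.96. Here q = [sqrt(B² - 4AC) - B]/(2A), A = 2n, B = -b - c + (2n - b + c)d and C = -cd(1 - d). The exact McNemar p is 2 × P(X ≤ min(b, c)) with X ~ Binomial(b + c, 1/2). For 8 v 2 it is 2 × (1 + 10 + 45)/1024 = 0.109.

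| b v c | Difference | Tango 95% CI (points) | Exact McNemar p |
|---|---|---|---|
| 6 v 0 | +20 | +6.4 to +37.3 | 0.031 |
| 7 v 1 | +20 | +1.9 to +38.6 | 0.070 |
| 8 v 2 | +20 | -0.8 to +39.9 | 0.109 |
| 9 v 3 | +20 | -2.9 to +41.2 | 0.146 |
| 10 v 4 | +20 | -4.7 to +42.4 | 0.180 |
| 11 v 5 | +20 | -6.4 to +43.5 | 0.210 |
| 12 v 6 | +20 | -7.9 to +44.7 | 0.238 |

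At other assumed sizes with 80% v 60%, 20 malignant patients (5 v 1) give -4.9 to +43.7 and 50 (13 v 3) give +4.8 to +35.2.

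**4. How much could the reference matter?** The introduction gives thoracoscopy with biopsy 94% sensitivity. Then 30 biopsy-malignant patients imply 30/0.94 = 31.9 true malignancies, so about 2 missed. Take the extreme in which both are cytology-positive (at 60%, 2 × 0.6 = 1.2 would be expected). Counting them as malignant makes cytology 20/32 = 62.5%. Starting from 8 v 2:

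- neither is pCLE-positive: 24/32 = 75.0%, 8 v 4, difference +12.5 (CI -9.3 to +33.4);
- one is pCLE-positive: 25/32 = 78.1%, 8 v 3, difference +15.6 (CI -5.2 to +35.6).

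Leaving such patients out tends to favour pCLE, and counting them as malignant favours cytology.

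**The case against.** The strongest reply is that this is an exploratory, proof-of-concept study with no success threshold for aim 2. Sensitivities can be read from counts, and two sensitivities with exact intervals would be a reasonable minimum. The point difference is the same in every split of step 3; only its precision changes. Much of this stands, and it lowers the severity. It does not remove the gap. The protocol uses the exploratory label to explain the missing sample size, and the label does not supply an analysis for a stated aim. Nor does the plan mention even those two sensitivities.

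The illustration is also open to challenge. The 80% has no source in the documents, and the 60% is an upper figure for repeated sampling while the design describes a single thoracocentesis step. That stands, and the conclusion does not rest on these figures. At 7 v 1 the interval excludes zero while the exact p is 0.070. This reflects a score interval set beside a conservative exact test: the mid-p value is 0.070 - 8/256 = 0.039, which agrees with the interval. It is not a defect of the plan.

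A reader might infer three stronger things that the documents do not support.

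- *That the study cannot address aim 2 at all.* All three procedures are done in the same patients, so the paired table can be built.
- *That the plan has no rule for a positive pCLE.* Table 1 is not shown and may contain one. Nothing suggests that it also holds the comparison with cytology.
- *That Fisher's test is wrong.* It is valid for the association it names.

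**Conclusion.** The point holds: the stated analysis does not address the second aim, because cytology is not an input to it. This follows from the text alone and needs no numerical assumption. The size is illustrative. With 30 malignant patients at 80% v 60%, the same +20 points can have a lower 95% limit anywhere from about +6 to -8, so raw percentages alone would not show how firm the comparison is. These counts are assumed and do not predict the trial's result.

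Severity is SHOULD-FIX. A reader might rate it higher because half of the stated aims is affected. The study is exploratory, however, the design already yields the paired data, and nothing is lost beyond recovery. The text mixes past and future tense, so it is unclear whether results have been seen. That bears on how the added analysis is labelled, not on whether it is needed.

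**What to change.** Add a per-patient paired analysis for aim 2.

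1. **Population and reference.** Use patients with malignant thoracoscopic biopsy histology.
2. **pCLE result.** Use one binary mini-invasive call per patient, from table 1 if it gives the rule. Say how the two endoscopists' ratings become one call. Label the rule post hoc if results have been seen.
3. **Main result.** Cross-tabulate the call against same-session cytology. Report both sensitivities with exact 95% intervals and the paired difference with a 95% interval (for example Tango). Any McNemar p-value is secondary.
4. **Non-evaluable pCLE and inconclusive cytology.** Count them as not positive and give their numbers.
5. **Cytology-positive, biopsy-negative patients.** Report them separately and do not simply count them as cytology false positives. Add a sensitivity analysis counting them as malignant. State that the main analysis may favour pCLE and this one cytology.
6. **Fisher tests.** Keep them as descriptive. Specificity with exact intervals is an optional addition.

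The cost is plan wording and a few short tables, plus a written positivity rule if table 1 lacks one. No extra patients or procedures are needed. The downside is that pCLE sensitivity may look less favourable once non-evaluable images count as not positive, and a post hoc rule carries less weight.

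### Invasive pCLE sites are biopsied one for one, but the only planned test has no site-matched comparison and makes no allowance for several sites per patient

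*Combined protocol and SAP*

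**What the plan says.** The Study design section divides the procedure into four parts. In part two, the mini-invasive one, "the probe was blindly introduced in the pleural space through the Boutin's needle". No biopsy matched to that spot is described.

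In part three the probe is applied to the parietal pleura under vision. The rule for choosing sites depends on how the pleura looks: "If macroscopic abnormalities were noticed, pCLE was performed on the affected zones". Otherwise: "In the absence of macroscopic abnormality, three random sites were selected". On scoring, the section says only: "The same criteria were rated by the same two investigators". It then states: "Finally, biopsies were systematically performed on the same sites for pathological diagnosis".

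The Statistical analysis section names one test: "The Fisher's exact test was used to analyze the link between pCLE qualitative variables and the final histological diagnosis". Its only other statement is that multiple testing is not adjusted for. It gives no unit of analysis, no rule for combining sites and no separation of parts two and three.

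The accuracy aim is: "To determine the sensitivity of mini invasive pleural pCLE compared to pleural fluid cytological analysis". Invasive pCLE is named in neither aim. On sample size: "No formal sample size calculation can be performed for such exploratory study".

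**The concern.** Part three is the only place where the visual criteria can be checked against tissue from the spot that was imaged. The plan collects that tissue but specifies no analysis that uses the pairing.

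The word final and the singular diagnosis most naturally mean one diagnosis per patient. Under that reading, take a malignant patient with three random sites and tumour at one of them. If pCLE reads all three sites correctly, two of the three readings still disagree with the patient's diagnosis. A criterion that reads tissue well would then look weaker than it is wherever disease is patchy.

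Under the other reading, in which each rating is tested against the histology of its own site, the pairing is right but the test is not. Fisher's exact test assumes independent observations, and sites within one patient share the same disease, staining, operators and session.

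What is at stake is how far part three can support or reject the individual criteria.

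**Working it through.** The plan states no sample size, power, alpha or accuracy figure for this comparison, so there is nothing of its own to reproduce. The check has two steps: list the readings that the text allows, then size the effect on assumed values.

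**Readings that the text allows for part three**

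| Rating unit | Reference | Consequence |
|---|---|---|
| Site | Patient's diagnosis | Correct benign readings at uninvolved sites are set against a malignant label; sites within a patient are also not independent |
| Site | That site's histology | Pairing is right; Fisher's test ignores clustering within patient |
| Patient (one rating) | Patient's diagnosis | Neither problem arises, but the matched tissue is unused and the way several sites become one rating is not stated |

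**Size under the first reading**

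Inputs, all assumed because the documents give none of them for this study: site-level sensitivity Se and specificity Sp, and p, the share of imaged sites in malignant patients that bear tumour.

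Apparent sensitivity against the patient's diagnosis = p × Se + (1 − p) × (1 − Sp).

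With Se = Sp = 0.90:

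- p = 0.80: 0.80 × 0.90 + 0.20 × 0.10 = 0.74
- p = 2/3: 0.667 × 0.90 + 0.333 × 0.10 = 0.63
- p = 0.50: 0.50 × 0.90 + 0.50 × 0.10 = 0.50

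With Se = Sp = 0.80, the same values of p give 0.68, 0.60 and 0.50.

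Fisher's test looks at association, so the contrast between malignant and benign patients matters more than the sensitivity alone. In benign patients the positive rate is 1 − Sp = 0.10. The true contrast is 0.90 − 0.10 = 0.80. It becomes 0.74 − 0.10 = 0.64, 0.63 − 0.10 = 0.53 and 0.50 − 0.10 = 0.40. In general it is p × (Se + Sp − 1), so the contrast shrinks in proportion to p.

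With site-matched histology the expected sensitivity is 0.90 whatever p is.

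**Size under the second reading**

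For a proportion estimated from three sites per patient with within-patient correlation ρ, the variance is multiplied by 1 + (3 − 1)ρ = 1 + 2ρ. That runs from 1 (ρ = 0) to 3 (ρ = 1). The documents give no value for ρ and no number of affected zones per patient, so this is only the possible range for three equal sites. Ignoring it makes P values too small when ρ is positive.

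**The case against.** **The text does not confirm a mismatch.** A reader might infer that the plan definitely tests site ratings against the patient's diagnosis. It never says that the diagnosis is the patient's, nor that the criteria are scored per site. Table 1, cited for the criteria and their interpretation, was not in the text available for this review, so any scoring detail in it could not be checked. This objection stands: the defect is an unspecified unit and reference. It does not rescue the plan, because no allowed reading both uses the matched tissue and handles several sites per patient.

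**The accuracy aim is elsewhere.** A reader might infer that the main result is biased. It is not. The aim compares mini-invasive pCLE with cytology, and a patient-level reference is the right one for both. This stands in full and limits the point to part three.

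**The illustration leans on a subset.** Where abnormalities are seen, the probe goes to them, so uninvolved sites in malignant patients arise mainly with three random sites or when an abnormal zone proves benign. The share of such patients is unknown. This stands, and it is why the figures are illustrative only.

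**Calling a patient positive if any site is positive would remove the problem.** With one involved site of three, patient-level sensitivity would be 1 − 0.10 × 0.9² = 0.92, but the false-positive rate in patients with no involved site would be 1 − 0.9³ = 0.27 (same assumed 90%, independent sites). The plan contains no such rule, so this can neither defend nor criticise it.

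**Site-matched data would explain why blind pCLE misses a cancer.** This is tempting, but the documents do not support it. The blind site has no described matched biopsy, and a negative part-three reading at a different tumour-bearing site cannot show that the blind probe was on tumour.

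**Conclusion.** The point holds as a gap in the analysis of part three. The design yields a biopsy for each imaged site, and the single planned test specifies neither a site-matched comparison nor any allowance for several sites per patient.

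The direction of the harm is clear under each reading that treats sites as observations: a diluted association if the reference is the patient's diagnosis, and overstated precision if correlated sites are counted as independent. The size is not known. The fall from 90% to between 74% and 50% rests wholly on assumed accuracy and on an assumed 80% to 50% of imaged sites bearing tumour, and it applies only if per-site ratings are tested against a patient-level diagnosis.

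The conclusion on mini-invasive pCLE against cytology is not affected. For an exploratory study this should be corrected because the remedy is cheap and uses tissue that is already taken, but it does not undermine the study's stated aims.

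**What to change.** State the unit and the reference separately for each part.

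- **Part three:** record the criteria for each imaged site, label each biopsy with the same site number, and compare each site's rating with that site's own histology. Use a method that allows for clustering by patient, for example GEE or a bootstrap that resamples patients. No sample size is fixed, so if few patients are included, use a small-sample correction with GEE.
- **Part two and cytology:** compare per patient with a defined patient-level final diagnosis.
- **Reporting:** present the two parts separately and do not pool them. Do not use part-three results to assign a cause to individual part-two misses.

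The cost is a site number on the rating form and the specimen pot, slightly more handling in pathology and a little more analysis. No extra biopsy is needed, since the imaged sites are already biopsied.

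The protocol mixes past and future tense, so the procedures may already be complete. If site labels were kept, only the analysis changes. If they were not, the matching cannot be recovered, and the report should give this as a limitation of the part-three results.
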